6.1 Primary Objectives

6.1.1 Pilot Phase

The goal of the pilot study is to establish that standard FNA samples contain enough cells to complete the proposed assays. The number of epithelial cells obtained from a typical FNA will be

modeled using a Poisson distribution, with parameters estimated from the first 10 subjects (5 malignant, 5 benign).

If the expected probability of obtaining the required 300 cells is less than 99%, additional passes of the needle will be taken to achieve this goal.

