5.1 FNA Procedure: For Suspicious lesions

Women ages 18 or older who have been recommended for ultrasound guided core biopsy for a suspicious breast lesion at the Green Spring Johns Hopkins Imaging site will be recruited into the study.

The FNA will be performed on one ultrasound visible lesion per patient, using the method described by Fabian et. al. [21, 22] which is standard at Johns Hopkins and used by the breast imagers. When recommended for the core biopsy, participants are asked to abstain from aspirin and other medications/supplements related to blood clotting and platelet function outlined in the eligibility criteria for a week prior to the procedure. For the procedure, 1% lidocaine local anesthesia is delivered at the skin (1 to 5 cc) followed by deeper infiltration (about 5 to 10 cc) of 1% lidocaine with or without 1:100,000 epinephrine at the site of each lesion; this will also be used for the core needle biopsy, which will immediately follow the FNA procedure. When more than one eligible lesion is visible in the same patient, one random lesion will be selected.

NOTE: Buffered lidocaine may be used per investigator preference/institutional standard. Next, the FNA procedure itself is performed by sampling the lesion with a 22 to 25 gauge needle attached to a 5 ml syringe with 2-3 passes through each lesion using ultrasound guidance thus confirming accurate targeting. Additional lidocaine may be given if needed for discomfort. The core needle biopsy using standard of care procedures will then occur.

The standard post biopsy instructions, both verbal and written will be provided to all patients. An ice pack is applied to the breast(s) following the procedure, and the subjects are asked to wear a firm sports bra (alternatively, compression wraps or firm bandages may be used).

In our present study, where 1 FNA procedure consists of 2 to 3 passes of the needle into the suspicious lesion, the mean pain rating is 1-1.5 (on a scale of 10); this is consistent with publications from the University of Kansas and the Johns Hopkins study [21, 22]. We may also use a buffered 1% lidocaine so as to minimize the burning sensation associated with unbuffered lidocaine. With our present technique, we are experiencing an average epithelial cell yield of 10,000 cells, and about 10% of samples contain less than 5,000 cells. DNA methylation studies can be performed with as low as 300 cells.

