5.3 Quantitative and Multiplexed Methylation

DNA will be extracted and analyzed by the Cepheid's Breast Cancer Detection cartridge and QM-MSP as previously described in the laboratory of [name] (10;11). Both the cartridge and QM-MSP permit analysis of multiple methylated genes using the same aliquot of DNA with as few as 300 epithelial cells to provide a quantitative estimate of the level of methylation in each gene that exists in each sample.

The cells will be smeared onto 4 uncharged slides. The slides, in batches of 10, will be stained with Quik-Dip by the [name] lab and epithelial cells will be counted. The slides will be taken to the cytopathologist to determine their diagnosis (benign or malignant), the cytopathologist will create a report, deidentify the slide with a lab number and keep the lab personnel blinded to the diagnosis.

Cells on the stained slide will be lysed using a custom lysis buffer. An aliquot of the lysate will be used in the automated methylation assay. The results of the methylation assay will be sent to the cytopathologist to compare with standard histopathology based diagnosis report of the H and E stained section of the tumor.

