5.6 Study design

Because this study represents the first use of FNA samples in the GeneXpert cartridge, it will necessary to establish that: 1) a standard FNA sample yields enough cells to perform the assay, and 2) lock down the decision rule for calling a sample malignant based on DNA methylation levels, before 3) obtaining an unbiased estimate of performance. Accordingly, the study will be divided into pilot, training and test phases, respectively, to accomplish these 3 tasks.

Pilot: FNA specimens from the first 5 malignant and 5 benign tumors will be smeared onto uncharged slides, stained and the epithelial cells will be enumerated to ensure that the procedure results in collection of adequate number of cells (>300). If not, additional passes of the needle (up to 5) will be instituted for the FNAs that follow. The remaining cells, if any, will be stored as slides for future optimization of the assay, if needed.

Training Set: A sample size of 80 cases with invasive disease and 80 controls with benign disease is proposed. With the projected incidence of methylated gene markers in benign disease tissue at higher than threshold values at 10%, we project a specificity of 80%. If needed, we will test other tumor specific genes known to us to improve the panel such that a panel of up to 10 genes will function with $>90\%$ specificity.

Test Set: A sample size of 80 cases with invasive disease and 80 controls with benign disease is proposed. . If sensitivity and specificity exceeding 90% is achieved in the training set, we will enroll patients for FNAs for the Test set.

We propose to use DNA methylation as biomarkers in cells obtained by fine needle aspiration in a total of 330 women who have suspicious breast lesions recommended by ultrasound guided core needle biopsy for definitive diagnosis. If needed, IRB approval will be requested for the addition of new patients to compensate for FNAs with sparse or no cells, so that projected numbers are fulfilled.

6. Statistical Considerations

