The above study plan will recruit 5 women with benign disease and 5 women with malignant disease to undergo FNA prior to core biopsy in the Pilot phase. 80 evaluable subjects with benign disease and 80 with malignant disease will be recruited for FNA prior to core biopsy in Training phase. An additional 80 women with benign disease and 80 women with malignant disease will be recruited for the Test phase if the criteria for the assay are met in the Training set. If not, the assay will be fine-tuned further in the lab with modifications to increase sensitivity and specificity.

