6.2.1 Sample Size Considerations

Our sample size considerations are motivated by the need for precise estimates of performance, so that an apparently successful model can be carried forward with confidence. Our current methylated marker panel achieves both sensitivity and specificity higher than 90% for distinguishing between normal/benign and malignant disease when evaluated using QM-MSP, and so sample size requirements are calculated at that level. At the proposed sample size, at a sensitivity and specificity of 90%, the estimation errors for the conditional specificity are controlled at +/-10%.

In addition to 10 pilot patients, we will recruit 80 subjects in each group, in each of the two major phases (training and test). This number was selected to control the precision of the confidence intervals on sensitivity and specificity. Specifically, with a sample size of 80 in each group, and sens/spec of 90%, the performance can be estimated to within 10% percentage points (lower, 95% confidence bound =80%), a level of confidence we feel is appropriate for this study.

We estimate that 40%-50% of suspicious lesions will turn out to have malignant disease after path exam of the core biopsy, in which case the limiting factor in obtaining the necessary 330 lesions will be collecting 165 malignant cases. Assuming the lower value of 40% malignancy, we expect to have to enroll $165/0.4=413$ patients in order to obtain at least the required 165 cases. At the more extreme ends of the sampling distribution, there is a 10% chance that we can obtain the necessary cases in as few as 382 enrollments, and conversely a 10% chance of falling short even with 447 enrollments. Accordingly, after enrolling 382 subjects we will calculate rates of malignant and benign disease, and estimate total enrollment requirements, and continue enrollment as needed.

7. Adverse Event Reporting

Subjects will be contacted by phone 1-2 days post-FNA and core biopsy to assess adverse events. There is some complexity in this reporting as a core needle biopsy will immediately follow the FNA. The cause, FNA vs core biopsy, of the AE will be inseparable; therefore, determining which process led to the AE will be impossible.

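### The pilot models cell counts as Poisson, which the protocol's own yields rule out; its 99% check depends only on the mean and cannot detect sparse or empty FNAs.

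*Combined protocol and SAP*

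**What the plan says.** Section 6.1.1 (Pilot Phase) states that cell counts will be "modeled using a Poisson distribution, with parameters estimated from the first 10 subjects (5 malignant, 5 benign"). The trigger for action is worded "If the expected probability of obtaining the required 300 cells is less than 99" percent.

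Four other places bear on this:

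- Section 5.1 describes experience with the present technique: "we are experiencing an average epithelial cell yield of 10,000 cells, and about 10% of samples contain less than 5,000 cells". It puts the assay minimum at 300 cells.
- Section 5.6 describes the pilot differently. There, "epithelial cells will be enumerated to ensure that the procedure results in collection of adequate number of cells (>300"), with additional needle passes to follow if that is not achieved. It does not say how many low counts amount to failure.
- Section 5.6 also provides for extra patients "to compensate for FNAs with sparse or no cells", without giving a rate.
- The opening of section 6 counts "80 evaluable subjects with benign disease and 80 with malignant disease will be recruited for FNA prior to core biopsy in Training phase", so FNAs that fail for lack of cells fall outside the training total.

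The plan contains no allowance for overdispersion or excess zeros, no check of the Poisson fit, and no criterion based on the observed proportion of adequate samples.

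**The concern.** The Poisson distribution has one parameter and forces the variance to equal the mean. The spread that section 5.1 reports is far too wide for that. The misfit affects the decision because the 99% criterion concerns the lower tail, and under a Poisson the tail is fixed once the mean is known. The individual counts, including any at or near zero, affect the result only through their average.

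The pilot exists to show that an ordinary FNA gives enough material. If a few percent of FNAs are empty, the 6.1.1 check would still report near-certain adequacy. The shortfall would then appear later as non-evaluable samples and replacement enrolment. The empty samples cause that cost; the model hides it at the one stage designed to find it.

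**Working it through.** **Inputs.** From 5.1: mean 10,000, about 10% of samples below 5,000, assay minimum 300. From 6.1.1: Poisson model, 99% criterion, 10 pilot subjects. From 6.2.1: 165 malignant cases at 40% malignancy. The rate of empty FNAs is not documented; 1%, 2%, 5% and 9.9% are assumed. Section 5.1 caps the rate at about 10%, since an empty sample is also below 5,000.

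**1. Can a Poisson give the figures in 5.1?** Its SD is √10,000 = 100, so 5,000 lies (10,000 − 5,000)/100 = 50 SDs below the mean. P(X < 5,000) is numerically zero, against the stated 10%. A single Poisson would need a mean of about 5,091 to put 10% below 5,000.

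No alternative model is needed to show the conflict. Cantelli's inequality gives P(X ≤ mean − a) ≤ v/(v + a²). With a = 5,000, 0.10 ≤ v/(v + 25,000,000), so v ≥ 2,500,000/0.9 = 2.78 million. The SD is at least 1,667 and the variance at least 278 times the Poisson value.

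If separate means are fitted for malignant and benign lesions, the 10% can be matched only by coincidence (for example, equal-sized groups with means near 5,060 and 14,940). The check would still use means alone.

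**2. When is the 99% check met?** P(X ≥ 300) is 0.9889 at a mean of 341 and 0.9903 at 342. The threshold is therefore a fitted mean of about 342 (343 if the requirement is more than 300). For example, nine empty FNAs and one of 10,000 cells have a mean of 1,000. The Poisson then gives essentially 100% adequacy when 1 of 10 was adequate.

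**3. What does realistic spread do?** A negative binomial matched to 5.1 has size 5.32 and a variance-to-mean ratio of about 1,880. Holding that size fixed (an assumption), the adequacy at lower means is:

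| Mean | Poisson P(≥300) | Negative binomial P(≥300) |
|---|---|---|
| 342 | 0.990 | 0.560 |
| 500 | 1.000 | 0.824 |
| 1,000 | 1.000 | 0.984 |

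The negative binomial reaches 99% at a mean of about 1,116. A matched lognormal needs 969 and gives 0.522 at 342.

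**4. What if some FNAs are empty?** Each scenario keeps the overall mean at 10,000 and 10% of samples below 5,000. Non-empty counts follow a gamma distribution with mean 10,000/(1 − π), where π is the empty fraction.

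| Assumed empty | True adequacy | Probability that the 6.1.1 check is met | Probability that any of 10 pilot counts is below 300 | Expected enrolment, 412.5/(1 − π) |
|---|---|---|---|---|
| 1% | 99.0% | >0.9999 | 9.6% | 417 |
| 2% | 98.0% | >0.9999 | 18% | 421 |
| 5% | 95.0% | >0.9999 | 40% | 434 |
| 9.9% | 90.1% | >0.9999 | 65% | 458 |

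The third column comes from 400,000 simulated pilots, pooled and by group. It is easy to see why: in these scenarios a group mean falls below 342 essentially only if all five of its FNAs are empty. At 9.9% that has probability 2 × 0.099⁵ ≈ 0.00002 over the two groups. The last column starts from the plan's own 165/0.4 = 412.5, given there as 413 "patients in order to obtain at least the required 165 cases". It assumes that non-evaluable FNAs are replaced.

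**5. What can direct counting show?** Ten adequate samples out of 10 give an exact two-sided 95% CI of 69% to 100% (lower limit 0.025^(1/10) = 0.692). With 10 pilot and 160 training FNAs, the chance of at least one failure is 1 − (1 − p)^170: 82%, 97%, 99.98% and about 100% at p = 1%, 2%, 5% and 10%. Even 170 out of 170 has a lower limit of 0.025^(1/170) = 97.9%. A one-sided 95% bound of 99% needs ln 0.05/ln 0.99 = 298.1, so 299 FNAs without a failure.

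**The case against.** If the yields in 5.1 hold and there is no separate group of empty samples, the check gives the right answer. The matched negative binomial puts only about 2.5 in 10 million samples below 300, so any sensible model would be satisfied. That stands. The error needs an empty or sparse fraction that the documents mention only as a contingency. At the assumed 1% the result is borderline correct, and 9.9% is an extreme case in which nearly every sample below 5,000 is empty. The negative binomial contrast at a mean of 342 likewise applies only if yield falls to about 1/29 of the reported figure.

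Section 5.6 also enumerates individual counts, and it can be read as a complement to 6.1.1. If any single low count were treated as failure there, that check would fire in 40% of pilots at 5% empty and 65% at 9.9%. This softens the point without removing it, because 5.6 sets no trigger and 6.1.1 can report adequacy on the same ten counts.

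The enrolment cost is not caused by the Poisson choice. The plan already allows for replacement patients and for re-estimation after 382 enrolments. Three of the four totals lie inside its 382 to 447 range. Finally, ten direct counts are weak too. That is correct, and it is why the estimate should carry on into training.

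**Conclusion.** The concern holds and is minor. The Poisson model in 6.1.1 is incompatible with the yields in 5.1 by a factor of at least 278 in variance, and this needs no assumption beyond those two figures. The 99% criterion reduces to a fitted mean of about 342 cells or more and takes no account of spread.

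How far it misleads depends on an undocumented rate of empty FNAs. At assumed rates of 2%, 5% and 9.9% it would declare the 99% target met when true adequacy is 98.0%, 95.0% and 90.1%. The decision rule and the sensitivity and specificity estimators are not affected. What suffers is the pilot's feasibility conclusion and early warning of extra enrolment.

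**What to change.** In 6.1.1, replace the Poisson probability with the number of the 10 pilot FNAs that reach the required count and an exact binomial 95% CI. Say plainly that 10 samples cannot establish 99%.

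Update the estimate during training using every FNA attempted, not only those that become evaluable. Report it as an estimate with its interval and do not claim that 99% has been shown.

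Reconcile 6.1.1 with the enumeration in 5.6 so that one pre-stated check governs, and settle whether the requirement is at least 300 or more than 300. The number of low counts that prompts action, and the needle-pass response, are for the investigators to decide.

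The cost is mainly SAP wording. Section 5.3 already has slides stained by the "lab and epithelial cells will be counted", so the only new task is to keep counts from non-evaluable FNAs. Two consequences should be accepted openly. The stated adequacy will look less favourable, and if the investigators chose to act on any single failure, that would happen in 9.6% of pilots even when true adequacy is exactly 99%.

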5.4 STRAT4 subtyping assay

A cell lysate from a second unstained slide will be analyzed in the automated STRAT4 (ER/PR/HER2/Ki67) assay cartridge.

STRAT4 results will be compared to standard estrogen receptor (ER), progesterone receptor (PR), human epidermal growth factor receptor 2 (HER2) and Ki67 (ER/PR/HER2/Ki-67) by IHC/FISH performed routinely by the pathlab for comparative accuracy of the markers.

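### The pilot tests the 300-cell minimum on the whole FNA yield, but the methylation assay receives only an aliquot of the lysate from part of that yield

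*Combined protocol and SAP*

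**What the plan says.** Section 6.1.1 sets the aim: "The goal of the pilot study is to establish that standard FNA samples contain enough cells to complete the proposed assays". The variable it defines is the epithelial count of a whole specimen, which is "modeled using a Poisson distribution, with parameters estimated from the first 10 subjects (5 malignant, 5 benign"). The trigger for extra passes is "If the expected probability of obtaining the required 300 cells is less than 99" per cent. Section 5.6 uses the same unit: on the pilot slides, "the epithelial cells will be enumerated to ensure that the procedure results in collection of adequate number of cells (>300").

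Section 5.3 describes what happens between collection and assay. It gives 300 epithelial cells as the lower limit for the DNA aliquot analysed by the cartridge and by QM-MSP. Then:

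- "The cells will be smeared onto 4 uncharged slides";
- cells on the stained slide (singular) are lysed;
- "An aliquot of the lysate will be used in the automated methylation assay".

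Other uses draw on the same specimen. Section 5.4 states: "A cell lysate from a second unstained slide will be analyzed" for STRAT4. Section 5.5 names FNA lysate, or FFPE sections, as material for the QM-MSP comparison. The summary in 1.3.3 describes two cartridges for the 10 genes.

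No section gives a per-slide minimum, the fraction of lysate loaded, or an adjustment of the 300 for the split.

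**The concern.** The number 300 appears at two levels. In 5.3 it is an input requirement of the methylation assays. In 5.6 and 6.1.1 it is compared with everything the needle collects. Since the specimen is divided at least twice in between, a whole-FNA total of 300 does not deliver 300 cells to the assay.

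Cell adequacy is the pilot's only goal, and 5.6 describes this study as the first use of FNA samples in the cartridge. If the rule passes when input is too low, under-loaded samples could reach the training phase, where the methylation threshold is set, or prove unevaluable and need replacing.

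**Working it through.** **Inputs**

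- Pass rule: P(count ≥ 300) ≥ 0.99, Poisson, whole FNA (6.1.1).
- Split: 4 slides (5.3). Equal split and one slide lysed for methylation are assumptions.
- Fraction of slide lysate loaded, *a*: not stated; range 10% to 100% assumed.
- Reported yield: mean 10,000 cells, about 10% of samples below 5,000 (5.1).

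The plan derives no required mean yield from its rule, so there is no figure of its own to reproduce.

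**Step 1. Where the rule passes as written.** Solving P(X ≥ 300) = 0.99 for a Poisson count gives a mean of 341.8 cells per FNA. One of four equal slides then holds 341.8 / 4 = 85.4 cells on average, and the chance that it holds 300 is effectively zero.

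**Step 2. What the same standard needs at assay input.** A Poisson count split at random remains Poisson, so the required whole-FNA mean is 341.8 × 4 / *a*.

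| Fraction loaded, *a* | FNA cells giving 300 at input (1,200 / *a*) | Whole-FNA mean for 99% assurance |
|---|---|---|
| 100% | 1,200 | 1,367 |
| 50% | 2,400 | 2,734 |
| 25% | 4,800 | 5,468 |
| 10% | 12,000 | 13,670 |

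Any mean from about 342 up to 1,367 passes the written rule yet fails the 99% standard on one slide, before aliquot loss. At a mean of 1,000 the rule passes with near certainty, but one slide reaches 300 with probability 0.001; at 1,200 that probability is 0.51.

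**Step 3. Shortfall at the reported yield.** A Poisson with mean 10,000 puts essentially no probability below 5,000, against the reported 10%, so wider models are needed. Three were fitted to the two facts in 5.1:

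- lognormal: log-SD 0.459, log-mean 9.105;
- gamma: shape 5.32, mean 10,000;
- normal: SD = 5,000 / 1.2816 = 3,902.

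The normal puts 0.52% of its probability below zero cells. It is therefore also shown with that part removed: (p − 0.0052) / (1 − 0.0052), where p is the plain normal probability.

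| Fraction loaded | Lognormal | Gamma | Normal | Normal, negatives removed |
|---|---|---|---|---|
| 100% | 0.0006% | 0.03% | 1.2% | 0.69% |
| 50% | 0.2% | 0.6% | 2.6% | 2.1% |
| 25% | 8.5% | 8.7% | 9.1% | 8.7% |
| 10% | 73% | 72% | 70% | 69% |

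Entries are the share of FNAs with fewer than 300 cells at assay input, that is, whole-FNA yield below 1,200 / *a*. In every row the whole-FNA Poisson rule would pass, because the mean is 10,000.

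**Step 4. Break-even fraction.** An average FNA puts 10,000 / 4 = 2,500 cells on a slide, so 300 enter the assay if *a* ≥ 300 / 2,500 = 12%. An FNA of 5,000 cells puts 1,250 on a slide and needs *a* ≥ 24%.

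**The case against.** The strongest reply is that the dangerous range is far from the reported experience. A mean between 342 and 1,367 is roughly 7 to 29 times below the 10,000 cells in 5.1. If the whole lysate of one slide is loaded, every fitted model that excludes negative counts puts the shortfall below 1%. This stands, and it limits the severity. It does not settle the matter, because 5.3 says an aliquot is loaded and gives no fraction.

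Safeguards also exist. Section 5.3 counts epithelial cells on the slides before lysis. Section 6 asks for 80 evaluable subjects per group in training. Section 5.6 allows patients to be added to make up for sparse FNAs, and actin serves as internal control (1.3.3). These limit the harm, but none corrects the pilot rule or states a numerical input cut-off.

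The number of slides lysed is unclear: 5.3 speaks both of slides being stained and of the stained slide. Pooling slides would shrink the factor of 4. Section 5.4 keeps at least one slide unstained for STRAT4, so pooling would not remove the factor.

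Two stronger readings are tempting but unsupported:

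- A reader might infer that the reported yield already breaches the plan's 1% limit on a full slide, because a plain normal model gives 1.2%. Of that, 0.52 percentage points lie below zero cells; without them the figure is 0.69%.
- A reader might infer that every assay, STRAT4 included, would receive a quarter or less of its minimum. The 300 is given only for the methylation assays, and no minimum is stated for STRAT4. Even for methylation, a quarter depends on exactly one slide being lysed.

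**Conclusion.** The point holds as a minor one. The decision rule in 5.6 and 6.1.1 tests a whole-specimen count, whereas 5.3 sets the 300-cell limit at methylation-assay input. As written, the rule cannot distinguish adequate from inadequate input: with an equal split and one slide lysed, it passes from a mean of about 342 cells per FNA where about 1,367 or more is needed.

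The practical size is open because it turns on the unstated aliquot fraction. At the reported yield the shortfall is under 1% of FNAs with the full slide lysate and becomes material at about a quarter of the lysate or less (about 9% at 25%, about 70 to 73% at 10%). These figures rest on the equal split, one slide lysed, and yield models fitted to the two facts in 5.1. The documents do not show that under-loading will occur, or that it would produce false negatives.

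**What to change.** In 5.6 and 6.1.1, define the pilot count as the epithelial cells available at methylation-assay input: the count on the slide or slides lysed, multiplied by the fraction of lysate loaded. Apply the 300-cell, 99% criterion to that quantity, estimated from the per-slide counts of the 10 pilot subjects.

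Reconcile 5.3, 5.6 and 6.1.1 so that they agree on how many slides are lysed for methylation and what fraction of the lysate is loaded. If two cartridges or QM-MSP share one lysate, state the fraction for each.

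The change concerns only the quantity tested; what follows when the criterion is missed is outside this point. The cost is a few sentences of wording. Slides are already counted, so recording counts per slide adds almost no work, and the sample size is unaffected.
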